k. **Tumor Assessment:** Tumor assessments are required for all subjects within 28 days prior to enrollment. Baseline and on-treatment tumor assessments for solid tumors by iRECIST should include CT with contrast of chest, abdomen, and pelvis and other known sites of disease at each time point. Bone scan and positron emission tomography (PET)/CT should be performed only if clinically indicated. Baseline and on-treatment tumor assessment for lymphoma by RECIL 2017 should be done using CT scan with contrast and PET/CT of neck, chest, abdomen, and pelvis and other known sites of disease at each time point. Please refer to Section 8 for requirements regarding disease assessment. Tumor assessments must be performed at screening and at the following intervals until disease progression is confirmed: approximately every 8 weeks through week 24 (e.g., C3D1, C5D1, C7D1), every 12 weeks up to year 2 (prior to cycles 10, 13, 16, 19, 22, 25, 28 and 31), and then every 6 months (prior to cycles 37, cycle 43, etc.) up to conclusion of the study. Confirmatory scans should be performed at least 4 weeks (>28 days), but no longer than 8 weeks after initial documentation of an objective response. Subjects who discontinue study treatment for reasons other than disease progression (e.g., AE or withdrawal of consent) will be monitored for radiologic response until start of another anti-cancer therapy, or disease progression, withdrawal of consent or death.

l. **PK/immunogenicity (i.e., ADA) and cytokine sampling (Dose Escalation Cohorts):** PK, ADA, and cytokine time points for collection of samples are outlined in supplementary tables in Section 6.1.1. ([Table 6](#), [Table 7](#) and [Table 8](#)). Blood volumes required are provided in the SLM. PK, ADA, cytokine samples should not be collected from infusion port for drug delivery i.e., recommend having a separate line in the opposite arm for sample collection. If subject has positive ADA test on D1 of cycle 13, then follow up predose samples for PK/ADA should be collected every ~90 days on D1 of subsequent treatment cycles until ADA resolves to baseline. If ADA positivity is detected within 7-30 days after the last dose of SL-279252, then follow up testing for PK/ADA should be performed at monthly intervals until ADA resolves to baseline.

m. **Correlative laboratory studies:** Refer to supplementary [Table 9](#) for details in Section 6.1.2 plus see the SLM for amount of blood needed.

- *Complement*

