When using iRECIST, the definitions of measurable and non-measurable lesions still follow RECIST 1.1. The principles used to establish an objective tumor response when using iRECIST are largely unchanged from RECIST 1.1, however, responses assigned using iRECIST have a prefix of “i” (e.g., “immune” complete response [iCR]) to differentiate them from responses assigned using RECIST 1.1.

The major change is the concept of resetting the bar if RECIST 1.1 progression is followed at the next assessment by tumor shrinkage. This adaptation accounts for instances where an increase in tumor burden, or the appearance of new lesions, does not reflect true tumor progression. Therefore, iRECIST requires confirmation of progression.

Confirming Progression: iRECIST requires the confirmation of progression and uses the terms iUPD (unconfirmed progression) and iCPD (confirmed progression). Confirmatory scans should be performed at least 4 weeks after iUPD. iCPD is confirmed if further increase in tumor burden, compared to the last assessment, is seen as evidenced by one or more of the following criteria:

- Continued increase in tumor burden (from iUPD) where RECIST 1.1 definitions of progression had been met (from nadir) in target, non-target disease or new lesions.
 - Progression in target disease worsens with an increase of at least 5 mm in the absolute value of the sum
 - Continued unequivocal progression in non-target disease with an increase in tumor burden
 - Increase in size of previously identified new lesion (s) (an increase of at least 5 mm in the absolute value of the sum of those considered to be target new lesions) or additional new lesions
- RECIST 1.1 criteria are met in lesions types (target or non-target or new lesions) where progression was not previously identified, including the appearance of additional new lesions.
- If iUPD is not confirmed at the next assessment, then the appropriate response will be assigned (iUPD if the criteria are still met, but no worsening, or iSD, iPR or iCR if those criteria are met compared to baseline).

New Lesions: New lesions should be assessed and measured as they appear using RECIST 1.1 criteria (maximum of 5 lesions, no more than 2 per site, at least 10 mm in long axis (or 15 mm in short axis for nodal lesions) and recorded as New Lesions-Target (NLT) and New Lesion-Non-Target (NLNT) to allow clear differentiation from baseline target and non-target lesions.

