New lesions may either meet the criteria of NLT or NLNT to drive iUPD (or iCPD). However, the measurements of target lesions should NOT be included in the sum of measures of original target lesions identified at baseline. Rather, these measurements will be collected on a separate table in the eCRF.

Progressive disease is confirmed in the New Lesion category if the next imaging assessment, conducted at least 4 weeks (but not more than 8 weeks) after iUPD confirms further progression from iUPD with either an increase of at least 5 mm in the absolute value of the sum of NLT OR an increase (but not necessarily unequivocal increase) in the size of NLNT lesions OR the appearance of additional new lesions.

iRECIST Time Point Response Table

Target Lesions	Non-Target Lesions	New Lesions	Time Point Response (TPR)	
			No prior iUPD	Prior iUPD
iCR	iCR	No	iCR	iCR
iCR	Non-iCR/Non-iUPD	No	iPR	iPR
iPR	Non-iCR/Non-iUPD	No	iPR	iPR
iSD	Non-iCR/Non-iUPD	No	iSD	iSD
iUPD with no change OR decrease from last TP	iUPD with no change OR decrease from last TP	Yes	NA	NLs confirms iCPD if NL were previously identified and increase in size (≥ 5 mm in SOM for NLT or any increase for NLNT) or number. If no change in NLs (size or number) from last TP, remains iUPD
iSD	iUPD	No	iUPD	Remains iUPD unless iCPD confirmed based in further increase in size of NT disease (need not meet RECIST 1.1 criteria for unequivocal PD)
iUPD	iUPD	No	iUPD	Remains iUPD unless iCPD confirmed based on: further increase in SOM of at least 5 mm, otherwise remains iUPD
iUPD	iUPD	No	iUPD	Remains iUPD unless iCPD confirmed based on further increase in: previously identified T lesion iUPD SOM ≥ 5 mm and/or NT lesion iUPD (prior assessment need not be unequivocal PD)

Target Lesions	Non-Target Lesions	New Lesions	Time Point Response (TPR)	
			No prior iUPD	Prior iUPD
iUPD	iUPD	Yes	iUPD	Remains iUPD unless iCPD confirmed based on further increase in: 
 • previously identified T lesion iUPD SOM ≥ 5 mm and/ • previously identified NT lesion iUPD (prior assessment need not be unequivocal PD) • size or number of new lesions previously identified
Non-iUPD/PD	Non-iUPD/PD	Yes	iUPD	Remains iUPD unless iCPD confirmed based on: 
 • increase in size or number of new lesions previously identified

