## 8. EFFICACY ANALYSES

The efficacy analysis will be based on the All Treated population and/or Efficacy Evaluable population, as appropriate. The efficacy endpoints include ORR, CBR, time to response (TTR), DOR, tumor size change from baseline for target lesions, PFS, and OS.

Response assessment will be based on the iRECIST for solid tumors and RECIL 2017 for lymphoma. Radiographic disease assessment must be performed at screening, and at the following intervals until a disease progression is confirmed: every 8 weeks through week 24, every 12 weeks

up to year 2 and then every 6 months up to conclusion of the study. Disease assessment window is +/- 1 week. Confirmatory assessments should be performed at least 4 weeks ( $\geq$  28 days) after the initial documentation of an objective response or an unconfirmed disease progression. Subjects who discontinue study treatment for reasons other than disease progression will be monitored for radiologic response until start of new anti-cancer therapy, disease progression, withdrawal of consent or death.

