### 8.1.3 Derivation of Best Overall Response based on iRECIST

The best overall response based on iRECIST is defined as the best overall response among all post-baseline timepoint assessments until the first iCPD or the last assessment if an iCPD has not been observed. Based on the investigator assessment of overall response at all post-baseline assessments, the best overall response will be determined according to the following:

- iCR > iPR > iSD > iCPD (iUPD if no iCPD) > NE
- iCR = iCR must be confirmed at least 4 weeks later.
- iPR = iPR must be confirmed at least 4 weeks later.
- iSD = at least one iSD or better  $\geq$  49 days after the first dose date and not qualifying for an iCR or iPR. The minimum interval from the first dose date for the best response of iSD is 8 weeks minus 7 days to allow for the visit windows of  $\pm$  7 days (49 days).

- iCPD = iUPD must be confirmed by a subsequent assessment at least 4 weeks later to have iCPD.
- iUPD = iUPD is not confirmed by a subsequent assessment at least 4 weeks later and not qualifying for iSD or better.
- Clinical deterioration will not be considered as documented disease progression.

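### Protocol 16.6.3 gives conflicting time limits for confirming new-lesion progression, and its 8-week limit fits neither the scan schedule nor the SAP

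*Protocol*

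**What the plan says.** Protocol Appendix 16.6.3 addresses confirmation of new-lesion progression in three places.

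- **Confirming Progression:** "Confirmatory scans should be performed at least 4 weeks after iUPD". No upper limit is given. The criteria listed there include "Increase in size of previously identified new lesion (s) (an increase of at least 5 mm in the absolute value of the sum" of the target new lesions, and additional new lesions.
- **New Lesions:** progression in this category is confirmed if "the next imaging assessment, conducted at least 4 weeks (but not more than 8 weeks) after iUPD confirms further progression from iUPD", with growth or additional new lesions.
- **Time point response table:** growth in size or number of previously identified new lesions confirms iCPD. No time limit is given.

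Scans are due "approximately every 8 weeks through week 24 (e.g., C3D1, C5D1, C7D1), every 12 weeks up to year 2", then every 6 months (footnote k of the Schedule of Assessments, Protocol 6.1 to 6.4). Footnote b allows one week either side. Footnote k also gives a 4 to 8 week window for a confirmatory scan, but only after an objective response.

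SAP Section 8 repeats the visit window ("Disease assessment window is +/- 1 week") and asks for confirmation of a response or an unconfirmed progression at 28 days or more, with no maximum. SAP 8.1.3 says "iUPD must be confirmed by a subsequent assessment at least 4 weeks later to have iCPD". SAP Section 12 lists no departure from the protocol on this point.

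**The concern.** The upper limit stands in one sentence and for one lesion category. Everything else in the two documents is open-ended. The schedule was not built around the limit: its shortest nominal interval is exactly 8 weeks, so any net delay passes it, and from week 24 the interval is longer by design.

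This reaches the analysis because SAP 8.1.3 derives best overall response from the investigator's time point assessments. If one investigator applies the New Lesions paragraph and another the general rule, the same images enter the database under different codes. Three outputs depend on the code:

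- **Event date.** SAP Table 5 dates a confirmed progression at the initial iUPD, but an unconfirmed one at the last iUPD. DOR uses the same rules (SAP 8.6).
- **Best-response category.** SAP 8.1.2 tabulates iCPD and iUPD separately.
- **Best-response cutoff.** SAP 8.1.3 stops collecting assessments at the first iCPD.

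Protocol 8.3 also relies on the 16.6.3 definition of confirmed progression, so the conflict is not only a matter of analysis.

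**Working it through.** **Reproducing the SAP's own window arithmetic.** Minimum time for iSD: 8 × 7 − 7 = 49 days, as in SAP 8.1.3. Two missed assessments: 2 × 8 + 1 = 17 weeks and 2 × 12 + 1 = 25 weeks, matching the 16+1 and 24+1 weeks under SAP Table 5. The same nominal dates and one-week window are used below.

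**Scan dates.** Day 1 of cycle c falls at week 4(c − 1). Cycles 3, 5 and 7 are weeks 8, 16 and 24. Cycles 10 to 31 in steps of three are weeks 36 to 120. Cycles 37 and 43 are weeks 144 and 168.

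**Interval between consecutive scans.** Each scan may move by up to 1 week, so the range is the nominal gap plus or minus 2 weeks.

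| iUPD found at | Nominal gap | Range | Share over 56 days |
|---|---|---|---|
| Week 8 or 16 | 8 weeks | 42 to 70 days | depends on scan days |
| Weeks 24 to 108 | 12 weeks | 70 to 98 days | 100% |
| Week 120 onward | 24 weeks | 22 to 26 weeks | 100% |

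**Share over 56 days in the 8-weekly phase.** The gap is 56 + (offset of second scan − offset of first scan), so it exceeds 56 whenever the second offset is the larger. The documents give no distribution of scan days. If offsets are uniform and independent (assumption):

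- no deviation: 0%, since 56 days meets the limit;
- offsets within 3 days: 21 of 7 × 7 = 49 pairs, 43%;
- offsets across the full 7 days: 105 of 15 × 15 = 225 pairs, 47%.

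These are shares of scan pairs, with no unscheduled scan in between.

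**Effect on the event date, an example.** New lesions are the only sign of progression at week 24 and have grown at week 36, and no further scan is done. Under the general rule, week 36 is iCPD and PFS ends at the initial iUPD, week 24. Under the New Lesions paragraph the gap of 84 days is too long, so week 36 is iUPD again. SAP 8.9.1 still counts an event, but Table 5 dates it at the last iUPD, week 36. The difference is 12 weeks. In the 8-weekly phase the corresponding shift is 57 to 70 days.

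**Effect on the best-response category.** This reaches only subjects with no earlier qualifying iSD or better, chiefly those with iUPD at week 8. A subject with iSD at weeks 8 and 16 keeps iSD whichever code is used later.

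**Under the SAP rule.** The shortest on-schedule gap is 42 days, which exceeds 28. Every on-schedule next scan can then confirm.

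**The case against.** A reader might infer that new-lesion progression seen on a late scan can never become iCPD under the protocol. The documents do not say that. The New Lesions sentence states when progression is confirmed, not that this is the only way. The general rule and the response table both let new-lesion growth confirm without a time limit. This objection stands: the fault is a contradiction, not a bar.

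A reader might also infer that an unconfirmed subject is readily reset by a later iSD, iPR or iCR, which would erase the PFS event. The response table does not support this as a usual outcome. Every iSD, iPR and iCR row requires no new lesions, so a subject whose new lesions have grown and persist stays at iUPD or iCPD. SAP 8.9.1 then counts iUPD as an event when later time points are all iUPD, when no further assessment is done, when treatment stops because the subject is not clinically stable, or when the subject dies of the cancer. What remains is the date.

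Third, confirmation need not wait for a scheduled visit. The general rule calls for confirmatory scans, and Protocol Section 8 lets the investigator image more often. The 4 to 8 week phrase can even be read as the timing instruction for such a scan. That lowers the frequency, but it does not remove the conflict: the schedule gives such a window for a response and none for iUPD.

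Lastly, target and non-target growth has no upper limit, so only subjects whose confirmation rests on new lesions are exposed.

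**Conclusion.** The concern holds as an unresolved contradiction within Protocol 16.6.3, and between its New Lesions paragraph and the SAP. Two investigators can both follow the protocol and classify the same scan differently.

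The 8-week limit is exceeded by none of the 8-weekly intervals on nominal dates, by about 47% if scan days are uniform and independent across the window, and by every on-schedule interval starting at week 24 or later. The first two figures bracket a quantity that the documents do not give. None is a share of subjects: that would need the frequency and timing of iUPD whose confirmation depends on new lesions, which is not stated.

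The consequences are limited to the iRECIST event date for PFS and DOR, the split between iCPD and iUPD, and the point at which best response stops being assessed. RECIST 1.1 results do not change, because SAP 8.2.1 maps iUPD and iCPD alike to PD. The point is worth correcting because iRECIST is the stated standard for the solid-tumour secondary endpoints and the remedy is a text change.

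**What to change.** Reconcile the Confirming Progression text, the New Lesions paragraph and the response table in Protocol 16.6.3 with footnote k of the Schedule of Assessments and SAP Sections 8 and 8.1.3, so that all give one confirmation window. State what is recorded when a scan falls outside it. Because Protocol 8.3 relies on the same definition, the choice of window for conduct belongs to the sponsor and is not proposed here.

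For the analysis, add one sentence to SAP 8.1.3: iCPD is derived with the existing rule, a subsequent assessment at least 4 weeks after iUPD with no upper limit, for all lesion categories and whatever the scan day. The sentence should also say how this applies where the investigator entered iUPD only because of the interval. Measurements of target new lesions already have their own eCRF table under 16.6.3. Growth of non-target new lesions rests on the investigator's reading.

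The cost is a clarifying text change and one derivation rule, and the analysis rule needs no added imaging. The small downside is that some confirmations will rest on a longer gap, up to 14 weeks in the 12-weekly phase and 26 weeks in the six-monthly phase, which the SAP as written already accepts.

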16.7 RECIL

Target Lesions: Target lesions should be selected from those with the largest size that can be reproducibly measured and should preferably represent multiple sites or organs. In most cases, lymph nodes can be considered target lesions if the lymph node's longest diameter is ≥ 15 mm. Extra-nodal lesions are selected as target lesions if they have a soft tissue component, based on their size, and the ease of reproducibility of repeated measurements, with a minimum measurement of the longest diameter of ≥ 15 mm.

Non-target Lesions: All other lesions including measurable lesions over and above the 3 target lesions should be identified as non-target lesions and should be recorded at baseline without the need to measure them. In certain anatomical sites (inguinal, axillary, and portocaval), normal lymph nodes may exist in a narrow, elongated form, and such nodes should not be selected as target lesions if alternatives are available. Non-target lesions should be reported as present, absent, or unequivocal progression.

Bone marrow: A bone marrow biopsy would be performed as a part of staging. In participants with positive FDG-PET uptake may obviate the need for a bone marrow biopsy. Participants with HL without FDG update in the bone marrow or presence of B-symptoms do not need a bone marrow biopsy at baseline, as bone marrow biopsy in this situation is extremely unlikely to modify stage.

16.7.1 Evaluation of Response

Complete Response: Complete disappearance of all target lesions by CT scan with complete normalization of FDG-PET (Deauville score 1–3 [see Appendix Section 16.4]) uptake in all areas and bone marrow biopsy negativity (if it was positive or unknown at baseline). If pretreatment PET scan was negative, all lymph nodes that measure ≥ 15 mm in the long axis should regress to < 10 mm. CR is also defined as achievement of a PR by CT scan ($> 30\%$ decrease in sum of longest diameters of target lesions) plus normalization of FDG-PET in FDG-avid lymphoma. Because many novel agents may alter glucose uptake and/or metabolism, normalizing FDG-PET imaging alone is not sufficient by itself to determine CR status unless accompanied with a significant decrease ($>30\%$) decrease in the sum of diameters. Accordingly, a reduction in the sum of diameters by $\leq 30\%$ with normalization of FDG-PET uptake should not be considered a CR unless documented by a negative tissue biopsy.

In cases where pretreatment baseline tumor burden is low, with only a few lesions measuring around 2 cm in longest diameter, treatment effect may shrink the long axis of a target lymph node to normal values of <10 mm. However, even though the lymph node is now within normal size range, consistent with CR, the percentage of diameter reduction may be $<30\%$ (less than PR). In these cases, a normalized diameter of “0 or resolved” should be used to calculate the sum of diameter, and therefore ensuring accurate response designation.

Partial Response: A $\geq 30\%$ decrease in the sum of longest diameters of target lesions but not a CR, positive FDG-PET (Deauville score 4–5), any bone marrow involvement, no new lesions. If one or more target lesions grew but the sum of the diameters remains $\leq 30\%$ of the baseline measurement, and no new lesions appear, the response should be designated a PR.

Minor Response: $\geq 10\%$ decrease in the sum of longest diameters of target lesions but not a partial response, any FDG-PET findings, any bone marrow involvement, no new lesions.

Stable Disease: $< 10\%$ decrease or $\leq 20\%$ increase in the sum of longest diameters of target lesions, any FDG-PET findings, any bone marrow involvement, no new lesions.

Progressive Disease: $> 20\%$ increase in the sum of longest diameter of target lesions; for small lymph nodes of < 15 mm posttherapy, minimum absolute increase of 5 mm and long diameter > 15 mm; appearance of new lesion; any FDG-PET finding; any bone marrow involvement; new or no new lesions.

Progressive Disease After Initial Response: after initial response, and in the absence of appearance of new lesions, progressive disease is defined as an increase of the nadir sum of diameters by $> 20\%$.

Response Assessment in Participants Receiving Immune-Modulating Agents, Including Checkpoint Inhibitors: to account for potential ‘pseudoprogression,’ immune-related response criteria should be used, requiring confirmation of progressive disease on two consecutive scans at least 4 weeks apart and inclusion of new lesion measurements in the total tumor burden.

Appearance of New Extranodal Lesion: A minimum of 1 cm in largest diameter of new extranodal lesions is required to confirm progressive disease. New smaller but suspicious lesions should be designated as equivocal; if later confirmed (by CT or biopsy) as due to lymphoma, the documented date of disease progression should be the date of identification as equivocal.

Disseminated Disease: The status of nontarget lesions should be accounted for before formulating the final response status. The International Working Group statement provides a recommended approach to response designation involving the best response of target and nontarget lesions.

16.7.2 Response Designations in Lymphoma Table

Target Lesions	Non-Target Lesions	New Lesions	Overall Response
CR	CR	No	CR
CR	Non-CR/Non-PD (PR, MR, SD)	No	PR
CR	Unevaluable	No	UE
CR	No	No	CR
PR	Unevaluable	No	UE
PR	CR, Non-CR/Non-PD	No	PR

Target Lesions	Non-Target Lesions	New Lesions	Overall Response
PR	No	No	PR
MR	Unevaluable	No	UE
MR	CR, Non-CR/Non-PD	No	MR
MR	No	No	MR
SD	Unevaluable	No	UE
SD	CR, Non-CR/Non-PD	No	SD
SD	No	No	SD
PD	Any	Yes or No	PD
Any	PD	Yes or No	PD
Any	Any	Yes	PD

PD = progressive disease

